8.2.6 Glycated Haemoglobin

Blood samples for assessment of glycated haemoglobin (HbA1c) will be collected at

timepoints as specified in the SoA ([Table 1](#)).

8.3 Adverse Events and Serious Adverse Events

The Investigator is responsible for ensuring that all staff involved in the study are familiar with the content of this section.

The definitions of an AE or SAE can be found in [Appendix B](#).

Adverse events will be reported by the participant (or, when appropriate, by a caregiver, surrogate, or the participant's legally authorised representative).

The Investigator and any designees are responsible for detecting, documenting, and recording events that meet the definition of an AE.

8.3.1 Time Period and Frequency for Collecting Adverse Event and Serious Adverse Event Information

Serious AEs will be recorded from time of signature of the ICF and all AEs will be collected after the participant has received the first dose of study drug. The collection of AEs/SAEs will continue throughout the treatment period and including the Follow-up Period.

If the Investigator becomes aware of an SAE with a suspected causal relationship to the study drug that occurs after the end of the clinical study in a participant treated by him or her, the Investigator shall, without undue delay, report the SAE to the Sponsor.

8.3.2 Follow-up of Adverse Events and Serious Adverse Events

Any AEs that are unresolved at the participant's last AE assessment in the study are followed up by the Investigator for as long as medically indicated, but without further recording in the eCRF. AstraZeneca retains the right to request additional information for any participant with ongoing AE(s)/SAE(s) at the end of the study, if judged necessary.

Adverse Event Variables

The following variables will be collected for each AE:

- AE (verbatim)
- The date and time when the AE started and stopped
- Maximum intensity
- Whether the AE is serious or not
- Investigator causality rating against the study drugs (yes or no)
- Action taken with regard to study drugs
- AE caused participant's withdrawal from study (yes or no)

- Outcome

In addition, the following variables will be collected for SAEs:

- Date AE met criteria for SAE
- Date Investigator became aware of SAE
- AE is serious due to
- Date of hospitalisation
- Date of discharge
- Probable cause of death
- Date of death
- Autopsy performed
- Causality assessment in relation to study procedure(s)
- Causality assessment to other medication

8.3.3 Causality Collection

The Investigator should assess causal relationship between study drug and each AE, and answer ‘yes’ or ‘no’ to the question ‘Do you consider that there is a reasonable possibility that the event may have been caused by the study drug?’

For SAEs, causal relationship should also be assessed for other medication and study procedures. Note that for SAEs that could be associated with any study procedure the causal relationship is implied as ‘yes’.

A guide to the interpretation of the causality question is found in [Appendix B](#) to the CSP.

8.3.4 Adverse Events Based on Signs and Symptoms

All AEs spontaneously reported by the participant or reported in response to the open question from the study site staff: ‘Have you had any health problems since the previous visit/you were last asked?’, or revealed by observation will be collected and recorded in the eCRF. When collecting AEs, the recording of diagnoses is preferred (when possible) to recording a list of signs and symptoms. However, if a diagnosis is known and there are other signs or symptoms that are not generally part of the diagnosis, the diagnosis and each sign or symptom will be recorded separately.

8.3.5 Adverse Events Based on Examinations and Tests

The results from the Clinical Study Protocol (CSP) mandated laboratory tests and vital signs will be summarised in the Clinical Study Report (CSR).

Deterioration as compared to baseline in CSP-mandated laboratory values and vital signs should therefore only be reported as AEs if they fulfil any of the SAE criteria, are the reason for discontinuation of treatment with the study drug or are considered to be clinically relevant as judged by the Investigator (which may include but not limited to consideration as to whether treatment or non-planned visits were required or other action was taken with the study drug, eg, dose adjustment or drug interruption).

If deterioration in a laboratory value/vital sign is associated with clinical signs and symptoms, the sign or symptom will be reported as an AE and the associated laboratory result/vital sign will be considered as additional information. Wherever possible the reporting Investigator uses the clinical, rather than the laboratory term (eg, anaemia versus low haemoglobin value). In the absence of clinical signs or symptoms, clinically relevant deteriorations in non-mandated parameters should be reported as AE(s).

Any new or aggravated clinically relevant abnormal medical finding at a physical examination as compared with the baseline assessment will be reported as an AE unless unequivocally related to the disease under study.

8.3.6 Hy's Law

Cases where a participant shows elevations in liver biochemistry may require further evaluation and occurrences of AST or ALT $\geq 3 \times$ ULN together with total bilirubin $\geq 2 \times$ ULN may need to be reported as SAEs. Please refer to [Appendix E](#) for further instruction on cases of increases in liver biochemistry and evaluation of HL.

8.3.7 Reporting of Serious Adverse Events

All SAEs have to be reported, whether or not considered causally related to the study drug, or to the study procedure(s). All SAEs will be recorded in the eCRF.

If any SAE occurs in the course of the study, then Investigators or other site personnel inform the appropriate AstraZeneca representatives within one day ie, immediately but **no later than 24 hours** of when he or she becomes aware of it.

The designated AstraZeneca representative will work with the Investigator to ensure that all the necessary information is provided to the AstraZeneca Patient Safety data entry site **within one calendar day** of initial receipt for fatal and life-threatening events **and within 5 calendar days** of initial receipt for all other SAEs.

For fatal or life-threatening AEs where important or relevant information is missing, active follow-up will be undertaken immediately. Investigators or other site personnel will inform AstraZeneca representatives of any follow-up information on a previously reported SAE within one calendar day ie, immediately but **no later than 24 hours** of when he or she becomes aware of it.

Once the Investigators or other site personnel indicate an AE is serious in the EDC system, an automated email alert is sent to the designated AstraZeneca representative.

If the EDC system is not available, then the Investigator or other study centre staff reports a SAE to the appropriate AstraZeneca representative by telephone.

The AstraZeneca representative will advise the Investigator/study centre staff how to proceed.

For further guidance on the definition of a SAE, see [Appendix B](#) of the CSP.

The reference document for definition of expectedness/listedness is the IB for the AstraZeneca drug AZD5718.

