Abbreviations: 5-LO = 5-lipoxygenase; ACR = albumin to creatinine ratio; AEs = adverse events; CCI [REDACTED]; CKD = chronic kidney disease; CSR = clinical study report; CCI [REDACTED]; DKD = diabetic kidney disease; CCI [REDACTED]; ECG = electrocardiograms; eGFR = estimated glomerular filtration rate; CCI [REDACTED]; CCI [REDACTED]; CCI [REDACTED]; CCI [REDACTED]; PK = pharmacokinetics; CCI [REDACTED];

SAEs = serious adverse events; SBP = systolic blood pressure

^a Will be reported outside of the CSR

Overall Design

This is a Phase 2b, randomised, double-blind, placebo-controlled, multi-centre, dose-ranging study to evaluate the efficacy, safety and PK of AZD5718 in participants with proteinuric CKD.

The study will be conducted in approximately 118 study centres across 12 countries.

Approximately 632 participants comprising of 67% DKD and 33% non-DKD participants will

be randomised 1:1:1:1 to receive once daily oral doses of [redacted] mg AZD5718, [redacted] mg AZD5718, [redacted] mg AZD5718, or placebo, for the first 12 weeks with an add-on therapy of 8 weeks of dapagliflozin for all participants, to have 158 participants per group. The plan is to have approximately 568 evaluable participants (142 per group) completing the study.

Disclosure Statement: This is a double-blinded placebo-controlled treatment study with 4 arms.

Number of Participants:

Approximately 632 participants will be enrolled to achieve 568 evaluable participants (142 per group).

Intervention Groups and Duration:

The study will include 4 intervention groups: [redacted] mg AZD5718, [redacted] mg AZD5718, [redacted] mg AZD5718, and placebo for the first 12 weeks followed by the addition of dapagliflozin to all participants from Week 12 to 20.

The study will include 4 periods:

- Screening Period of up to 4 weeks
- Treatment Period 1 consisting of 12 weeks where the participants will receive a once daily oral dose of the assigned dose of study drug to be taken with approximately 200 mL water in the morning with no restrictions on food intake.

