- Treatment Period 2 consisting of 8 weeks where the participants will receive a treatment of once daily oral dose of dapagliflozin 10 mg in addition to the assigned dose of study drug. Only participants still taking their assigned treatment from Treatment Period 1 will progress to Treatment Period 2. Any participant with urine albumin to creatinine ratio (ACR) < 30 mg/g at Week 12 will be excluded from Treatment Period 2. The eligibility check to enter Treatment Period 2 will be done at Visit 7 (Week 12) using the last available urine ACR result, calculated as the geometric mean of the replicated measurements using 3 sequential first morning urine voids.
- Follow-up Period of up to 4 weeks.

The study will include a total of 10 visits which includes 2 visits during the Screening Period, 5 visits during the Treatment Period 1, 2 visits during the Treatment Period 2, and 1 visit during the Follow-up Period.

The expected total study duration, including the Screening Period, for each participant will be at least 28 weeks.

Data Monitoring Committee: Not applicable

Statistical Methods

The primary efficacy variable is the change from baseline in urine ACR at 20 weeks compared to placebo. Primary analyses will be based on the per protocol population where participants are evaluated according to the randomised treatment assignment. Urine ACR will be log-transformed and analysed using mixed model repeated measures method. The analysis model will include the fixed categorical effects of stratification factor, treatment, visit, and treatment-by-visit interaction, plus the continuous covariates of baseline log (urine ACR) and baseline log (urine ACR)-by-visit interaction. An unstructured covariance structure will be used for the within-participant errors. A homogeneity assessment between the DM and the non-DM sub-populations will be performed.

The change from baseline in urine ACR at 12 and 20 weeks will be analysed using the Multiple Comparison Procedure Modelling approach. Multiple candidate dose response models will be assessed. The best fitting model based on Akaike's Information Criteria will be used as a reference for dose selection.

Efficacy on current standard of care will be based on the Full Analysis population up to Week 12. The change in urine ACR from baseline to Week 12 will be log-transformed and be analysed similarly as the primary variable.

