- ^l Phone call will occur after results from Screening Visit 1 are available and the participant is confirmed eligible in order to remind the participants to collect the first morning void urine samples and schedule the Screening Visit 2. If scheduled Visit 3 (Week 1) or Visit 7 (Week 12) will need to be delayed due to the need to repeat ABPM recording there is no need to repeat collection of the 3 urine samples.
- ^m Participants to collect first morning void urine samples on 3 consecutive days (ideally day of visit and each of the preceding 2 days [refrigerated overnight] which are returned on the day of visit). This collection may be repeated once during the course of screening.
- ⁿ Participants will be provided an ABPM cuff at Screening Visit 2 and Visit 6 (Week 8) and instructed to perform ABPM 24-hours before their next visit ie, Visit 3 (Week 1) and Visit 7 (Week 12), respectively. Site will be asked to call the participant the day prior to next visit as a reminder to complete assessments. The participant may also visit the site for APBM cuff placement 1 day before their next visit of scheduled assessment (ie, Visit 3 [Week 1] and Visit 7 [Week 12] respectively).
- ^o Sites should ensure that the validity criterion described in Section 8.2.5 is met prior to completing any other assessments at the visit. If the validity criterion is not met, the associated study visit may be rescheduled to allow for a repeat ABPM recording only if the rescheduled visit can be completed within the specified tolerance period for study visits:
- Visit 3: up to 72 hours following the originally scheduled visit for Visit 3 but no more than 32 days from Screening Visit 1
 - Visit 7: \pm 72 hours from Day 85
- If a repeat ABPM session is not possible, the study visit should proceed as indicated. In addition, the visit should also continue if the ABPM session does not meet the validity criterion after the repeat session.

^p Study drug refers to AZD5718/placebo during Treatment Period 1 and AZD5718/placebo + dapagliflozin during Treatment Period 2.

^q Site should follow-up directly with the participant via phone to remind the participant.

^r Participants to return all study drug dispensed at previous visits and only use the newly dispensed study drug. Participants should be reminded not to take study drug on the days of a study visit until instructed by the study site.

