2.3.2 Dapagliflozin

The safety profile of dapagliflozin has been evaluated in clinical development programmes for T2DM, T1DM, and heart failure. This includes more than 15000 participants treated with dapagliflozin for T2DM, more than 1000 participants treated with dapagliflozin for Type 1 Diabetes Mellitus (T1DM) and more than 2000 participants treated with dapagliflozin for heart failure. Overall, treatment with dapagliflozin 5 mg was similar to treatment with dapagliflozin 10 mg in both T1DM and T2DM. The safety profile of dapagliflozin was overall consistent across the studied indications. Dapagliflozin is authorised for treatment of T2DM, T1DM, and heart failure with reduced ejection fraction, and is under development for treatment in patients with CKD and heart failure with preserved ejection fraction.

The most commonly reported AEs associated with the use of dapagliflozin include genital infections, urinary tract infections, back pain, and polyuria. In addition, rash has been identified as an AE of unknown frequency in marketed use of dapagliflozin.

Diabetic Ketoacidosis

In the cardiovascular outcomes study, DECLARE, 8574 participants received dapagliflozin (FORXIGA) 10 mg and 8569 participants received placebo for a median exposure time of 48 months. Events of diabetic ketoacidosis (DKA) were reported in 27 participants in the dapagliflozin 10 mg group and 12 participants in the placebo group.

The events occurred evenly distributed over the study period. Of the 27 participants with DKA

events in the dapagliflozin group, 22 had concomitant insulin treatment at the time of the event. Precipitating factors for DKA were as expected in a T2DM population.

More detailed information about the known and expected benefits and potential risks of dapagliflozin may be found in the IB.

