6.3.3 Methods for Unblinding

The treatment code should not be broken except in medical emergencies when the appropriate management of the participant requires knowledge of the study drug. The Investigator documents and reports the action to AstraZeneca, without revealing the treatment given to the participant to the AstraZeneca staff.

AstraZeneca retains the right to break the code for SAEs that are unexpected and are suspected to be causally related to the blinded study drug and that potentially require expedited reporting to regulatory authorities.

For the administrative interim analysis, separate personnel with no other involvement in the study will be unblinded. A detailed description of the interim analysis to be conducted will be provided in the Statistical Analysis Plan (SAP).

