4.10.2 Adverse Events

Adverse events will be coded using MedDRA version 23.0 or later.

An AE (classified by preferred term) started during the treatment period will be considered a treatment-emergent adverse event if it was not present prior to the first dose of randomised treatment. An AE that starts more than 7 days after the last dose of study medication will not be counted as a treatment-emergent AE. AEs which worsen after the start of treatment will not be included as a treatment-emergent AE but will be recorded.

Adverse events (and also separately SAEs) will be summarised by study treatment group in incidence summaries by MedDRA SOC and PT. Adverse events will be assigned to the period where they start and will be summarised for the Safety Analysis Set, with selected outputs summarized for the Monotherapy Safety Analysis Set and Extended Safety Analysis Set with Week 12 flag. Serious adverse event collection will begin after the participant signs the informed consent document, and all AE collection will begin after the participant has received the first dose of the study drug. The SAE/AE collection will last until the end of the participant’s follow-up period.

All AEs will be listed and assigned to on/off treatment period as:

- Prior treatment: The SAE occurred before the first administration of study drug. Only applicable for SAEs.
- On treatment: The AE occurred on or after the first administration until 7 days after last dose of AZD5718 and/or dapagliflozin.
- Off treatment: The AE occurred more than 7 days after the last dose of study drug.

The number, percentage and percentage per participant exposure year (PEY) of participants reporting treatment-emergent AEs in each treatment group will be tabulated by SOC and PT; by SOC; by SOC, PT, and relationship to study medication as assessed by the Investigator. If more than one event occurs with the same preferred term for the same participant, the participant will be counted only once for that preferred term using the most severe and most related occurrence for the summarisation by severity and by relationship to the study medication.

The event rate per 100 PEY is defined as:

$$\left(\frac{\text{number of subjects with AE}}{\text{sum of days at risk for AE in treatment period} + 7 \text{ days}} \right) \times 365.25 \times 100$$

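### Two investigational drugs in Treatment Period 2, but one reference document for expectedness and one causality rating: attribution of serious and related events after Week 12 is blurred

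*Protocol*

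**What the plan says.** The synopsis describes three AZD5718 dose groups and placebo for 12 weeks, "followed by the addition of dapagliflozin to all participants from Week 12 to 20". Protocol Table 3 classes dapagliflozin as an experimental IMP alongside AZD5718 and placebo. Sections 2.2 and 2.3.2 refer to a separate dapagliflozin IB, and 6.7 calls both products study drugs.

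On causality, 8.3.2 lists one yes/no investigator rating against the study drugs. Section 8.3.3 words the question as "Do you consider that there is a reasonable possibility that the event may have been caused by the study drug". The additional causality items for SAEs cover only other medication and study procedures. Footnote p of the Schedule of Activities states: "Study drug refers to AZD5718/placebo during Treatment Period 1 and AZD5718/placebo + dapagliflozin during Treatment Period 2".

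On expectedness, 8.3.7 is explicit: "The reference document for definition of expectedness/listedness is the IB for the AstraZeneca drug AZD5718". Neither document names a reference for dapagliflozin.

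SAP 4.10.2 tabulates treatment-emergent AEs "by SOC, PT, and relationship to study medication as assessed by the Investigator".

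**The concern.** From Week 12 a suspected reaction may be due to either of two investigational drugs, but the plan applies single-drug rules to it.

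First, the expectedness rule sends every serious event to the AZD5718 IB, including one the investigator believes dapagliflozin caused. Protocol 2.3.2 says: "The most commonly reported AEs associated with the use of dapagliflozin include genital infections, urinary tract infections, back pain, and polyuria". It also describes diabetic ketoacidosis (DKA), with counts. If such a reaction is not in the AZD5718 IB, it is classed as unexpected although it is a recognised effect of the drug under suspicion. That can change whether the event is handled as a SUSAR.

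Second, the single rating does not say which drug was suspected. A reader of the relationship table will naturally take 'related' to mean related to AZD5718, the drug whose safety the study sets out to describe. After Week 12 that reading is not available.

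**Working it through.** This is mainly a check of the text. The plan states no figure to reproduce.

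**Step 1: what one rating can record.** With two drugs there are four possible judgements: neither, AZD5718/placebo only, dapagliflozin only, or both. One yes/no rating has two values. 'No' covers the first judgement and 'yes' covers the other three. The SAP's table inherits that merger.

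**Step 2: an event followed through the plan.** Take a serious urinary infection at Week 16 that the investigator attributes to dapagliflozin.

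| Stage | Rule | Result |
|---|---|---|
| Causality | 8.3.2, 8.3.3 | yes; drug not specified |
| Expectedness | 8.3.7 | judged against the AZD5718 IB |
| Known for dapagliflozin? | 2.3.2 | yes, urinary infection is named |
| SAP table | 4.10.2 | related to study medication |

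Neither IB is among the documents, so it is an assumption that the AZD5718 IB does not list the event. Hence the reaction can, not must, be classed as unexpected.

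**Step 3: whether the SAP separates the periods.** SAP 4.10 bases safety summaries on the Safety Analysis Set by default, and that set runs from Day 1 to the end of follow-up. For the Monotherapy and Extended sets, 4.10.2 and 4.10.3 name tables by SOC and PT and refer to selected outputs. No by-relationship table is named for either set. A participant is counted once per preferred term, using the most related occurrence. An infection rated unrelated in Period 1 and related in Period 2 therefore appears once, as related, for the whole study.

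**Step 4: whether the drugs are handled separately elsewhere.** They are. Overdose (8.4.1, 8.4.2), tablet records (6.4), discontinuation of either drug (7.1) and exposure (SAP 4.10.1) are all specified by drug. Causality and expectedness are not.

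**Step 5: scale.** Exposure in Period 2 = participants x 56 / 365.25.

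- All 632 planned: 632 x 56 / 365.25 = 96.9 participant-years.
- Planned evaluable 568: 568 x 56 / 365.25 = 87.1.
- The 340 who completed treatment (SAP 4.14): 340 x 56 / 365.25 = 52.1. Those who entered Period 2 but stopped early are not counted in this figure.

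The first figure is an upper bound on the planned exposure. The synopsis says "Any participant with urine albumin to creatinine ratio (ACR) < 30 mg/g at Week 12 will be excluded from Treatment Period 2", and participants who stop in Period 1 do not proceed either.

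**Step 6: one serious reaction for which the protocol gives counts.** DKA occurred in 27 of 8574 participants on dapagliflozin over a median of 48 months. The rate is 27 / (8574 x 4) = 0.79 per 1000 person-years. Assume that 67% of participants have DKD and only they are at risk, that the rate is constant and transfers to this population, and that the median exposure stands for the mean.

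- 632 entering: 0.67 x 632 = 423 with DKD, giving 64.9 person-years and about 0.05 expected cases. P(at least one) = 1 - exp(-0.051), about 5%.
- 340 entering: 228 with DKD, giving 34.9 person-years and about 0.03 expected cases. P(at least one) is about 3%.

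The documents give no rates for serious urinary or genital infection, so no total for affected SAEs can be computed.

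**The case against.** **The form may already ask per drug.** Section 8.3.2 uses the plural for causality and for action taken, and the eCRF cited in the SAP is not available. This stands in part: a per-drug field is unspecified, not excluded. The expectedness rule in 8.3.7 is a positive statement, however, and no field on a form would change it.

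**Footnote p is not a general definition.** It belongs to the drug-supply rows of the schedule. That is correct, but the point does not rest on it. Table 3 and Section 6.7 independently make dapagliflozin an IMP and a study drug, and 8.3.3 gives it no separate question.

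**The randomised comparison is intact.** All arms receive dapagliflozin in Period 2, so the contrast with placebo in AE rates still isolates AZD5718, and Period 1 is reported separately by SOC and PT. This stands. A reader might infer that dapagliflozin reactions distort the comparison between arms. The documents do not support that: these reactions can raise the related counts in every arm, placebo included, which blurs attribution without by itself producing bias.

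**Code breaks.** A reader might also infer that known dapagliflozin reactions would lead to unblinding, because 6.3.3 says "AstraZeneca retains the right to break the code for SAEs that are unexpected and are suspected to be causally related". That sentence goes on to limit the relation to the blinded study drug. Dapagliflozin is not blinded: Table 3, footnote a, makes placebo a comparator for AZD5718 alone. An event attributed only to dapagliflozin therefore does not meet the condition. The provision is also a right, not an automatic trigger. At most, a combined rating leaves the suspected drug unstated, and the sponsor can query the investigator.

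**Conclusion.** The point holds as one of attribution and safety classification. Section 8.3.7 applies one drug's IB to reactions suspected of another IMP, and nothing elsewhere in the protocol or SAP corrects it. The single rating specified in 8.3.2 and 8.3.3 leaves a related event in Period 2 unassigned between the drugs, and the SAP table carries that forward. The exception is a participant who is not taking both: 7.1 allows one drug to be stopped and the other continued, and some participants never enter Period 2.

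The size is modest. It is bounded by about 97 participant-years if all 632 entered Period 2, or about 87 for the planned 568. For DKA, fewer than 0.1 cases would be expected under the stated assumptions. The more certain effect is on the relationship table, which does not depend on rare events. The primary efficacy analysis is unaffected.

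The conclusion assumes that the eCRF follows the protocol text and that at least some recognised dapagliflozin reactions are missing from the AZD5718 IB. Neither can be checked from the documents. If the eCRF did collect causality per drug, the defect reduces to the wording of 8.3.7 and the layout of the SAP table.

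**What to change.** - **Protocol 8.3.7:** name the AZD5718 IB as the reference for events suspected of AZD5718/placebo, and the dapagliflozin IB for events suspected of dapagliflozin.
- **Protocol 8.3.2 and 8.3.3:** require causality to be rated separately for each IMP from the first dapagliflozin dose, and align the eCRF.
- **SAP 4.10.2:** tabulate relationship by drug for the Extended Safety Analysis Set with the Week 12 flag.
- **If only one rating was collected:** this matters because the SAP's third edition follows early termination. Split the relationship table at Week 12 and state that 'related' in Period 2 does not mean related to AZD5718.

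The cost is slightly more data entry at sites where the form does not already separate the drugs, a short addition to 8.3.7, and one extra table. The fallback needs no new data.
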